5.3.4 NIH Flow Cytometry Laboratory

Specimens received in the flow cytometry laboratory are accessible only to the flow cytometry laboratory team, as the laboratory door is locked and key access is only provided to the flow cytometry laboratory members. Additionally, the flow cytometry laboratory is set behind a set of double doors that are accessible only by badge/key card access.

5.3.5 Protocol Completion/Sample Destruction

All specimens obtained in the protocol are used as defined in the protocol. Any specimens remaining at the completion of the protocol will be stored in the conditions described above. The study will remain open as long as sample or data analysis continues. Samples from consenting subjects will be stored until they are no longer of scientific value or until a subject withdraws consent for their continued use, at which time they will be destroyed and data from the. Once primary research objectives for the protocol are achieved, intramural researchers can request access to remaining samples, provided they have an IRB-approved protocol and patient consent or an exemption from OHSRP.

The PI will report any loss or destruction of samples to the NCI IRB as soon as he/she is made aware of such loss. The PI will report destroyed samples to the IRB if samples become unsalvageable because of environmental factors such as a broken freezer or lack of dry ice in a shipping container, or if a patient withdraws consent. Samples will also be reported as lost if they are lost in transit between facilities or misplaced by a researcher. Freezer problems, lost samples, or other problems associated with samples will also be reported to the IRB, the NCI Clinical Director and the office of the CCR, NCI.

6 DATA COLLECTION AND EVALUATION

6.1 DATA COLLECTION

Data obtained on the study will be stored in C3D and Labmatrix.

The PI will be responsible for overseeing entry of data into an in-house password protected electronic system and ensuring data accuracy, consistency and timeliness. The principal investigator, associate investigators/research nurses and/or a contracted data manager will assist with the data management efforts. All data obtained during the conduct of the protocol will be kept in secure network drives or in approved alternative sites that comply with NIH security standards. Primary and final analyzed data will have identifiers so that research data can be attributed to an individual human subject participant.

All adverse events, including clinically significant abnormal findings on laboratory evaluations, regardless of severity, will be followed until return to baseline or stabilization of event.

An abnormal laboratory value will be recorded in the database as an AE **only** if the laboratory abnormality is characterized by any of the following:

- Results in discontinuation from the study
- Is associated with clinical signs or symptoms
- Requires treatment or any other therapeutic intervention
- Is associated with death or another serious adverse event, including hospitalization.
- Is judged by the Investigator to be of significant clinical impact
- If any abnormal laboratory result is considered clinically significant, the investigator will provide details about the action taken with respect to the test drug and about the patient's outcome.

End of study procedures: Data will be stored according to HHS, FDA regulations and NIH Intramural Records Retention Schedule as applicable.

Loss or destruction of data: Should we become aware that a major breach in our plan to protect subject confidentiality and trial data has occurred, the IRB will be notified.

6.2 DATA SHARING PLANS

6.2.1 Human Data Sharing Plan

What data will be shared?

I will share human data generated in this research for future research as follows:

 \underline{X} De-identified data in an NIH-funded or approved public repository.

 \underline{X} De-identified data in BTRIS

 \underline{X} De-identified or identified data with approved outside collaborators under appropriate agreements.

How and where will the data be shared?

Data will be shared through:

- X An NIH-funded or approved public repository. clinical trials.gov.
- X BTRIS
- X Approved outside collaborators under appropriate individual agreements.
- X Publication and/or public presentations.

When will the data be shared?

X Before publication.

 \underline{X} At the time of publication or shortly thereafter.

6.2.2 Genomic Data Sharing Plan

No large scale genomic data will be generated on this study.

6.3 **RESPONSE CRITERIA**

For the purposes of this study, patients should be re-evaluated for response every 6 weeks in the first 6 months, every 9 weeks until the end of year 2 and every 12 weeks thereafter. In addition to a baseline scan, confirmatory scans should also be obtained not less than 4 weeks following initial documentation of objective response.

Response and progression will be evaluated in this study using the new international criteria proposed by the revised Response Evaluation Criteria in Solid Tumors (RECIST) guideline (version 1.1)¹⁸. Changes in the largest diameter (unidimensional measurement) of the tumor lesions and the shortest diameter in the case of malignant lymph nodes are used in the RECIST criteria.

6.3.1 Definitions

Evaluable for toxicity: All patients will be evaluable for toxicity from the time of their first treatment with anetumab ravtansine.

Evaluable for objective response: Only those patients who have measurable disease present at baseline, have received at least one cycle of therapy, and have had their disease re-evaluated will be considered evaluable for response. These patients will have their response classified according to the definitions stated below. (Note: Patients who exhibit objective disease progression prior to the end of cycle 1 will also be considered evaluable.)

Evaluable Non-Target Disease Response: Patients who have lesions present at baseline that are evaluable but do not meet the definitions of measurable disease, have received at least one cycle of therapy, and have had their disease re-evaluated will be considered evaluable for non-target disease. The response assessment is based on the presence, absence, or unequivocal progression of the lesions.

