3.4 STUDY CALENDAR

1 cycle = 3 weeks (21 days)

Screening and baseline evaluations are performed per the timeframes indicated in sections 2.2 and 2.4 respectively.

On therapy assessments may be performed up to 5 days prior to indicated time; safety follow up may occur up to 7 days after indicated time; long term follow up phone calls may be performed within \pm 14 days of indicated time.

Dosing cycles after cycle 1 may be delayed for up to two weeks to accommodate schedule conflicts, Federal holidays and inclement weather, etc.

			Cycle 1	1	Sub	sequent Cyc	cles	Ender	Post Therapy Follow-up	
Procedure	Screening/ Baseline	Day 1	Day 8	Day 15	Day 1	Day 8	Day 15	Treatment	30 day safety follow up	Long term follow up
History and $PE^{\underline{1}}$	Х	Х	Х		X				Х	
Weight		Х			Х				Х	
Vital signs	Х	Х	Х		Х				Х	
ECOG Performance Score	Х									
Confirmation of dx and mesothelin expression	Х									
Imaging assessments ²	Х	Ever	y 6 week Y	ts (first 6 n year 2), eve	nonths), every ery 12 weeks t	9 weeks (un hereafter	til end of			
Echocardiogram	Х	Ever	y 6 weel	ks for the	first 6 months, thereafter	, then every	12 weeks			
12 lead ECG^3	Х	Х			X (cycle 2 only)				Х	
HBsAg, anti-HCV, anti-HIV	Х									
Ophthalmologic exam ⁴	Х				Х				Х	

			Cycle	1	Subsequent Cycles Fol		Post T Follo	herapy w-up		
Procedure	Screening/ Baseline	Day 1	Day 8	Day 15	Day 1	Day 8	Day 15	Treatment	30 day safety follow up	Long term follow up
CBC with differential, Hepatic Panel;	Х		Х	X 5	Х	X ⁵			х	
Acute Care Panel	Х									
PT/PTT	Х				Х				Х	
Urinalysis	Х				Х					
β-HCG in women of childbearing potential	Х				Х				X	
Optional biopsy	Х				Cycle 3 only					
Correlative Research Studies ⁶		Х			Cycle 3 only			X		
NIH Advance Directives Form	X ⁷									
Adverse Events						Continuous	assessment			
Concomitant Medications			Continuous assessment							
Phone calls q 3 months for survival status and new anti- cancer treatment										Х

¹ A complete physical exam is performed at screening. Thereafter, brief physical exams will be performed as per schedule above.

² The following imaging assessments will be performed: CT scan, MRI (if appropriate) and FDG PET. Assessments will continue until confirmatory scans for progressive disease have been obtained.

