6.3.4.3 Evaluation of Best Overall Response

The best overall response is the best response recorded from the start of the treatment until disease progression/recurrence (taking as reference for progressive disease the smallest measurements recorded since the treatment started). The patient's best response assignment will depend on the achievement of both measurement and confirmation criteria.

Target Lesions	Non-Target Lesions	New Lesions	Overall Response	Best Overall Response when Confirmation is Required*
CR	CR	No	CR	> 4 wks. Confirmation**
CR	Non- CR/Non-PD	No	PR	
CR	Not evaluated	No	PR	≥4 wks. Confirmation**
PR	Non- CR/Non- PD/not evaluated	No	PR	
SD	Non- CR/Non-	No	SD	Documented at least once ≥4 wks. from baseline**

For Patients with Measurable Disease (i.e., Target Disease)

	PD/not evaluated						
PD	Any	Yes or No	PD				
Any	PD***	Yes or No	PD	no prior SD, PR or CR			
Any	Any Any		PD				
*	See RECIST 1.1 manusc	ript for furthe	r details on what	is evidence of a new lesion.			
** (Only for non-randomize	d trials with re	esponse as prima	ry endpoint.			
***]	n exceptional circumsta lisease progression.	ances, unequiv	vocal progression	n in non-target lesions may be accepted as			
Note: I	Patients with a global deterioration of health status requiring discontinuation of treatment without objective evidence of disease progression at that time should be reported as " symptomatic deterioration ." Every effort should be made to document the objective progression even after discontinuation of treatment.						

For Patients with Non-Measurable Disease (i.e., Non-Target Disease)

Non-Target Lesions	New Lesions	Overall Response
CR	No	CR
Non-CR/non-PD	No	Non-CR/non-PD*
Not all evaluated	No	not evaluated
Unequivocal PD	Yes or No	PD
Any	Yes	PD
* 'Non-CR/non-PD' is preferred over an endpoint for assessment of efficate measured is not advised	• 'stable disease' for non-target disea ey in some trials so to assign this	se since SD is increasingly used as category when no lesions can be

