rate of 5% (p0=0.05) in favor of an improved response rate of 25% (p1=0.25). With alpha=0.10 (probability of accepting a poor treatment=0.10) and beta = 0.10 (probability of rejecting a good treatment=0.10), this first stage will enroll 13 evaluable patients (including patients treated at the safe dose found in the initial 6 patients), and if 0 of the 13 have a clinical response, then no further patients will be accrued. If 1 or more of the first 13 patients have a response, then accrual would continue until a total of 20 evaluable patients have been treated. As it may take up to several months to determine if a patient has experienced a response, a temporary pause in the accrual may be necessary to ensure that enrollment to the second stage is warranted. If there are 1 to 2 patients with a response out of 20 patients, this would be an uninterestingly low response rate. If there were 3 or more of 20 (15%) who experienced a response, this would be sufficiently interesting to warrant further study in later trials. Under the null hypothesis (5% response rate), the probability of early termination is 51%.

Assessment of serum samples and tumor biopsies will be exploratory and will be summarized descriptively.

The initial portion of the trial may require up to 6 patients who may not be included in the phase II portion if 2 or more of them experience DLTs at 6.5 mg/kg. The phase II portion may require up to 20 evaluable patients. Thus, if 5.5 mg/kg is the selected dose, then up to 26 evaluable patients may be required while if 6.5 mg/kg is selected, only up to 20 evaluable patients may be required. It is anticipated that approximately 50% of screened patients will have <5% mesothelin level and will not be treated on the protocol. Thus, in order to allow for 50% drop-outs for that reason as well as a small number of inevaluable patients, the accrual ceiling will be set at 55 patients. If 2 patients per month enroll on this trial, accrual would be expected to be completed in approximately 28 months.

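### Treated patients who are never re-evaluated drop out of the response rate and both Simon decisions, which can only push the rate upward; no all-treated analysis or non-responder rule is stated

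*Combined protocol and SAP*

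**What the plan says.** Section 6.3.1 defines who counts for response: patients with measurable disease at baseline who "have received at least one cycle of therapy, and have had their disease re-evaluated will be considered evaluable for response". Its one exception keeps patients with objective progression before the end of cycle 1. The same section makes every patient evaluable for toxicity from first treatment, so the restriction is specific to response.

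Section 8 states both Simon looks in evaluable patients. The first look is at 13, stopping if there are no responses. If there is at least one response, "then accrual would continue until a total of 20 evaluable patients have been treated"; 3 or more responses of 20 is a positive result. The accrual plan allows for screen failures on mesothelin "as well as a small number of inevaluable patients, the accrual ceiling will be set at 55 patients".

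Two provisions shrink the unassessed group. Footnote 2 of the Study Calendar (Section 3.4) says "Assessments will continue until confirmatory scans for progressive disease have been obtained". Section 6.3.4.3, on symptomatic deterioration, says "Every effort should be made to document the objective progression even after discontinuation of treatment". That section labels symptomatic deterioration but does not count it as non-response.

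No section gives a response rate over all treated patients, a rule for treated patients with no post-baseline assessment, or a sensitivity analysis for them.

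**The concern.** Whether a patient is re-evaluated depends partly on how the patient fares. The first scheduled scan is at 6 weeks (Section 6.3). Early death, clinical decline, a stop for toxicity or withdrawal can all come first. ECOG 2 patients who have already had platinum and a checkpoint agent are eligible (Sections 2.1.1.6 and 2.1.1.8), so such early losses are plausible. Under the written rule, a patient lost in this way without imaged progression disappears from the denominator and accrual continues until the place is filled.

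The excluded patients contribute no responses. The reported rate is therefore at or above the rate among everyone treated. The stated error rates are guaranteed only for patients who reach a re-evaluation. What is at stake is the go or no-go decision: the bar is 3 responses of 20, and at that size one or two replaced patients matter.

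**Working it through.** **Inputs from Section 8.** p0 = 0.05, p1 = 0.25, alpha = 0.10, beta = 0.10; first stage 13, stop at 0; total 20, success at 3 or more; stated early termination under p0 of 51%; ceiling 55 with 50% screen failure.

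**Assumed input.** d is the share of treated patients with no re-evaluation. The documents give no value, so a range is shown.

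**1. Reproduce the design.** With X1 ~ Bin(13, p) and X2 ~ Bin(7, p), independent,

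P(success) = P(X1=1)·P(X2≥2) + P(X1=2)·P(X2≥1) + P(X1≥3).

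- At p = 0.05: 0.3512 × 0.0444 + 0.1109 × 0.3017 + 0.0245 = 0.0156 + 0.0335 + 0.0245 = 0.0736.
- At p = 0.25: 0.1029 × 0.5551 + 0.2059 × 0.8665 + 0.6674 = 0.0571 + 0.1784 + 0.6674 = 0.903.
- Early termination at p0: 0.95^13 = 0.513, matching the stated 51%.

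An exhaustive search returns the same minimax design (0/13, 2/20). The design is correct for the rate in whichever population is counted.

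**2. Effect of the exclusion.** Let the true rate among treated patients be 5% and let unassessed patients be non-responders. The rate among evaluable patients is then 0.05/(1 − d). Putting this into the formula above:

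| d (assumed) | Rate among evaluable | Type I error | Early termination under null |
|---|---|---|---|
| 0 | 5.0% | 0.074 | 51.3% |
| 5% | 5.3% | 0.083 | 49.5% |
| 10% | 5.6% | 0.094 | 47.6% |
| 15% | 5.9% | 0.107 | 45.5% |
| 20% | 6.3% | 0.123 | 43.2% |

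Type I error reaches 0.10 at d = 12.3%.

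**3. What the accrual ceiling allows.** 55 × 0.5 = 27.5 treated places.

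- If 5.5 mg/kg is selected, up to 26 evaluable patients are needed, leaving 27.5 − 26 = 1.5 places. Then d = 1.5/27.5 = 5.5% and type I error is 0.084.
- If 6.5 mg/kg is selected, 20 are needed, leaving about 7 places. If all were used, d = 7/27 = 25.9% and type I error is 0.145. This is capacity, not a forecast.

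**4. Effect on a borderline result.** 3/20 is 15.0%. With two unassessed patients restored it is 3/22 = 13.6%; with five it is 3/25 = 12.0%.

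**5. Comparison with the cited phase I data.** Section 1.2.3.1, Table 2, reports 7 of 38 treated at the MTD (18.4%). The listed PR, SD and PD counts sum to 7 + 18 + 10 = 35, so 3 of 38 have no listed category yet stay in the denominator. Without them the rate would be 7/35 = 20.0%. The table gives no reason for the three, so this is not an estimate of d. It does show that the earlier rate was reported over all treated patients.

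**The case against.** The best counter-argument is that this is a choice of denominator, made in advance. Section 8 states the design for evaluable patients, Section 6.3.1 defines them, and for that population 0.074 and 0.903 hold. The trial seeks a preliminary estimate, and a positive result leads only to further study.

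The affected group is also narrow. Early objective progression counts, any re-evaluation after one cycle counts, and imaging is meant to continue after treatment stops. With 20 evaluable patients, one unassessed patient (d = 1/21) gives 0.083 and two (2/22) give 0.092; only at three (3/23) does the error reach 0.102.

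Replacement for response is inferred from accrual to 20 evaluable patients and from the ceiling's allowance. The word itself appears only in the toxicity rule of Section 3.1.3.

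Lastly, if 25% was meant for evaluable patients, moving to all treated costs power: 0.899 at d = 1%, already below 0.90.

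Most of this stands as a limit on size. No breach of 0.10 is demonstrated, the group is small by intent, and the power cost is real on that reading of p1. It does not remove the problem. Pre-specifying an exclusion does not make it independent of outcome, and the plan sets no limit on the unassessed fraction. Without an all-treated rate, a reader could not see the effect. Adding that rate only as a supplement would help transparency but would leave both decisions on the selected denominator.

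**Conclusion.** The concern holds. As written, treated patients with no re-evaluation are left out of the primary response rate and both Simon looks and are in effect replaced. The direction of the bias relative to all treated patients is upward. Its size depends on an unassessed fraction that the plan describes only as small.

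Assuming a 5% true rate among treated patients and no responses among the unassessed, type I error rises from 0.074 to between 0.083 and 0.123 for fractions of 5% to 20%. It stays within 0.10 up to about 12%, because the exact design has slack. The sample size and boundaries are not wrong. This should be fixed because the rule drives the main decision and the correction is cheap; it does not invalidate the design.

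**What to change.** Amend Sections 6.3.1 and 8 as follows.

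- Make the primary denominator at both looks (13 and 20) all eligible patients who received any anetumab ravtansine at the recommended phase 2 dose.
- Count a patient with no post-baseline disease assessment as a non-responder, without replacement for response.
- Keep the current evaluable set as a supportive analysis. Report both rates, with the number of treated patients not re-evaluated and the reasons.
- State that p0 = 5% and p1 = 25% refer to treated patients. The exact 0.074 and 0.903 then hold whatever the unassessed fraction.

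The cost is wording in two sections, with no new procedures and possibly a slightly lower reported rate. If 25% was meant for evaluable patients, the all-treated target is 0.25 × (1 − d), and power at 20 should be restated as 0.880, 0.854, 0.822 or 0.786 for d of 5%, 10%, 15% or 20%. The team should choose between these readings explicitly. Restating the power is enough; this point does not call for a larger trial.

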6.3.2 Disease Parameters

Measurable disease: Measurable lesions are defined as those that can be accurately measured in at least one dimension (longest diameter to be recorded) as ≥ 20 mm by chest x-ray, as ≥ 10 mm

with CT scan, or ≥ 10 mm with calipers by clinical exam. All tumor measurements must be recorded in millimeters (or decimal fractions of centimeters).

Malignant lymph nodes. To be considered pathologically enlarged and measurable, a lymph node must be \geq 15 mm in short axis when assessed by CT scan (CT scan slice thickness recommended to be no greater than 5 mm). At baseline and in follow-up, only the short axis will be measured and followed.

Non-measurable disease. All other lesions (or sites of disease), including small lesions (longest diameter <10 mm or pathological lymph nodes with \geq 10 to <15 mm short axis), are considered non-measurable disease. Bone lesions, leptomeningeal disease, ascites, pleural/pericardial effusions, lymphangitis cutis/pulmonitis, inflammatory breast disease, and abdominal masses (not followed by CT or MRI), are considered as non-measurable.

Note: Cystic lesions that meet the criteria for radiographically defined simple cysts should not be considered as malignant lesions (neither measurable nor non-measurable) since they are, by definition, simple cysts.

'Cystic lesions' thought to represent cystic metastases can be considered as measurable lesions, if they meet the definition of measurability described above. However, if non-cystic lesions are present in the same patient, these are preferred for selection as target lesions.

Target lesions. All measurable lesions up to a maximum of 2 lesions per organ and 5 lesions in total, representative of all involved organs, should be identified as **target lesions** and recorded and measured at baseline. Target lesions should be selected on the basis of their size (lesions with the longest diameter), be representative of all involved organs, but in addition should be those that lend themselves to reproducible repeated measurements. It may be the case that, on occasion, the largest lesion does not lend itself to reproducible measurement in which circumstance the next largest lesion which can be measured reproducibly should be selected. A sum of the diameters (longest for non-nodal lesions, short axis for nodal lesions) for all target lesions will be calculated and reported as the baseline sum diameters. If lymph nodes are to be included in the sum, then only the short axis is added into the sum. The baseline sum diameters will be used as reference to further characterize any objective tumor regression in the measurable dimension of the disease.

Non-target lesions. All other lesions (or sites of disease) including any measurable lesions over and above the 5 target lesions should be identified as **non-target lesions** and should also be recorded at baseline. Measurements of these lesions are not required, but the presence, absence, or in rare cases unequivocal progression of each should be noted throughout follow-up.

